11.2.1	General Approach	28
11.2.2	Primary & Secondary Endpoints	29
11.2.3	Other Pre-specified Analyses	29
12	Interim Analysis	30
13	Publications	30
14	protocol amendment history	30

STATEMENT OF COMPLIANCE

The trial will be carried out in accordance with International Conference on Harmonisation Good Clinical Practice (ICH GCP) and the following:

- United States (US) Code of Federal Regulations (CFR) applicable to clinical studies (45 CFR Part 46, 21 CFR Part 50, 21 CFR Part 56, 21 CFR Part 312, and/or 21 CFR Part 812)

National Institutes of Health (NIH)-funded investigators and clinical trial site staff who are responsible for the conduct, management, or oversight of NIH-funded clinical trials have

completed Human Subjects Protection and ICH GCP Training.

The protocol, informed consent form(s), recruitment materials, and all participant materials will be submitted to the Institutional Review Board (IRB) for review and approval. Approval of both the protocol and the consent form must be obtained before any participant is enrolled. Any amendment to the protocol will require review and approval by the IRB before the changes are implemented to the study. In addition, all changes to the consent form will be IRB-approved; a determination will be made regarding whether a new consent needs to be obtained from participants who provided consent, using a previously approved consent form.

PROTOCOL SUMMARY^{CT.GOV}

Title:

A pilot and feasibility study of a chronic pain self-management intervention for older adults incorporating podcasts and patient priorities.

Study Description:

This randomized pilot trial tests the feasibility of a community health worker (CHW)-delivered chronic pain self-management intervention for older adults ("STEP-UP"; Support, Training, and Education for Pain Self-Management – Using Podcasts) in a primary care setting.

Objectives*:

We will conduct a randomized (waitlist) pilot trial (n=40) in a Federally Qualified Health Center.

Endpoints*:

Primary Endpoint: Improvement in pain interference at 8 weeks (post-program)
Secondary Endpoints: physical functioning and global impression of change, and participant engagement and satisfaction (secondary outcomes) at 8 weeks

Study Population:

We will recruit 40 adults from a FQHC who are age 50+ with high-impact chronic pain.

Phase* or Stage:

Stage 1 (Behavioral Stage Model) Pilot Trial

**Description of Sites/Facilities
Enrolling Participants:**

Participants (N = 40) will be primarily recruited through Western Wayne Family Health Center's clinic in Inkster, Michigan.

**Description of Study
Intervention/Experimental
Manipulation:**

The STEP-UP chronic pain self-management intervention (Support, Training, and Education for Pain Self-Management – Using Podcasts) will feature an educational podcast series teaching core pain self-management skills. Podcasts will be supplemented by sessions with a Community Health Worker taking place at designated times over a 7-week period. The Community Health Worker will guide participants in a modified Patient Priorities of Care (PPC) approach to help them identify their values and priorities and develop goals that reflect these..

Study Duration*:

One year

Participant Duration:

Eight weeks

1 RATIONALE & BACKGROUND

1.1 Study Rationale

Our overall objective in this pilot trial is to develop and test the feasibility and preliminary efficacy of a pain self-management intervention (STEP-UP, or Support, Training, and Education for Pain Self-Management – Using Podcasts) that combines educational podcasts with community health worker-led sessions eliciting participants' values and related functional goals, and test its feasibility among primarily African American older adults at a Federally Qualified Health Center in a low-income community. STEP-UP is derived from the STEPS intervention, currently being tested in a large RCT (R01AG071511) but uses different educational tools (e.g., podcasts vs. videos in the original STEPS), includes a newly-developed component based on the Patient Priorities Care approach developed by Tinetti and colleagues, and is designed for delivery in a clinic-based (vs. community) setting.

1.2 Background

African American older adults disproportionately face barriers to managing persistent pain, including multimorbidity, chronic psychosocial stressors, and suboptimal pain care--all of which are rooted in structural racism. Yet opportunities to learn chronic pain self-management (CPSM) skills that can improve functioning and quality of life are scarce in underserved communities. Moreover, typical CPSM interventions provide little guidance for how older adults can work with their providers to help ensure that their pain treatment plans reflect their values, priorities, and health goals. We propose to address these gaps by developing the novel STEP-UP intervention (Support, Training, and Education for Pain Self-Management – Using Podcasts). STEP-UP will feature a podcast series teaching core pain self-management skills in a culturally-congruent manner. Podcasts will be accompanied by telephone sessions with a community health worker, who will guide participants in a modified Patient Priorities of Care (PPC) approach (originally developed for older adults with multiple chronic conditions) to identify their most important values and health outcome goals, and healthcare preferences. This information will inform self-management goals and will be shared with providers to promote patient-centered pain care.

1.3 Specific Aims

1. Develop and beta-test the STEP-UP chronic pain self-management intervention.
 - a) Create podcast episodes based on content from our existing STEPS and Positive STEPS CPSM interventions and lessons learned from podcast production in our ongoing RESET study.
 - b) Design community health worker session protocols and adapt the PPC process for the pain care context with expert and provider input.
 - c) Conduct a “beta” test of STEP-UP (n=5 participants) to refine content and processes.
2. Conduct a pilot RCT of STEP-UP.

- a) Using a waitlist randomized control design, deliver the STEP-UP intervention to 40 adults, age 50+ with high-impact chronic musculoskeletal pain, in a Federally-Qualified Health Center.
- b) Assess baseline to post-program changes in pain interference (primary outcome) and global impression of change in pain and functioning and participant engagement (secondary outcomes). Use mixed methods to evaluate key processes and explore mechanisms of effect.

Conduct qualitative interviews with clinic providers and administrators to: 1) identify factors affecting implementation, and 2) assess needs regarding a future provider-facing STEP-UP component. **JAN 11, 2023, NOTE: This will follow the pilot trial and the sampling plan will be informed by our experience during the trial; therefore, we will seek IRB approval for this element at a later date. ***

1.4 Risk/Benefit Assessment

1.4.1 Known Potential Risks

The risks of study participation are minimal, as we are testing an adaptation of a cognitive-behavioral intervention for chronic pain self-management, which does not involve drugs or devices and is non-invasive.

Below we list the potential risks, and in Section 1.3.b. we discuss how we will protect against/minimize each of these risks.

1. Psychological distress (FREQUENCY: Infrequent. SERIOUSNESS: Mild). A plausible but unlikely risk to participants is psychological distress during the course of the baseline or follow-up assessments or telephone sessions.

In the event of a participant expressing elevated distress as the result of an interaction, study staff will terminate the interaction (if deemed necessary) and/or offer psychological resources. We will have an updated list of Detroit-area resources for psychological support, which will be offered and mailed to participants as needed. Almost all of the survey questions (and all of the questions that are related to sensitive issues such as depressive symptoms) have been used in multiple prior studies, without noted problems. Participants will be informed as part of their informed consent process and immediately prior to each telephone interview that they can refuse to answer any of the questions or drop out of the study at any time. They will be asked if they would like to complete the interview over shorter sessions, if needed.

2. Breach of confidentiality during study activities (FREQUENCY: Rare, SERIOUSNESS: Mild).

Rigorous data security measures and staff training procedures will be put in place to minimize the risk of breach of confidentiality.

As part of their consent process, participants will be informed about the small risk of a breach of confidentiality. Email and text messages will only be used to reply to or contact participants if they choose this mode. For example, a participant may request a reminder text or email for a

scheduled survey or study visit, or they may indicate during enrollment that text or email is the best way to reach them to schedule telephone surveys or study visits. In this case, the study team may reach out to the participant via UM email or via text message. Survey responses or sensitive information will not be shared via email or text message. A secure UM email (Google) account will be created for the study and will be monitored by study staff.

All participant study information will be kept in a secure, HIPAA-compliant REDCap database within the University of Michigan. Additional study files will be secured in a HIPAA-compliant University of Michigan team Dropbox account.

Throughout the study, IRB guidelines and best practices in human subjects research will be followed to ensure the privacy and integrity of the information we collect. Any breach of confidentiality will be immediately reported to the PI and to the University of Michigan Health Sciences and Behavioral Sciences IRB. In addition, any complaints or concerns expressed to the study staff by participants, providers, or anyone else affected by this study will be immediately reported to the PI, and as appropriate, to the IRB.

All study staff, including community health workers, and research assistants will complete the online Social and Behavioral Research Best Practices course (<https://research-compliance.umich.edu/hrpp-education-resources>) which fulfills the NIH Good Clinical Practice requirement and the web-based University of Michigan's Responsible Conduct of Research Training Program, known as PEERRS (Program for Education and Evaluation in Responsible Research and Scholarship). Proof of their certification and completion of the training program will be kept on file. Training of staff will include information about the importance of privacy and confidentiality and specific techniques to maintain confidentiality of all information in the context of this study. Regular study team meetings will be used to ensure that all data quality and IRB policies and procedures are being followed.

All research data presented in reports, presentations, or manuscripts will be in aggregate and/or de-identified form only.

3. Physical Injury (FREQUENCY: infrequent, SERIOUSNESS: Mild)

Another possible risk is minor physical injury from doing physical activity that is encouraged by the STEP-UP program. Participants are encouraged to engage in physical activity of their choice, at a level that is comfortable for them. As with any physical activity, it is possible that participants could experience an injury while doing physical activity, like muscle strain. To minimize this risk, the STEP-UP Community Health Worker will guide participants in increasing activity levels slowly and will encourage them to check with their doctor if they do not know whether a specific activity is appropriate.

1.4.2 Known Potential Benefits

This intervention for chronic pain self-management will incorporate evidence-supported strategies to promote improved pain coping, and therefore has the potential for beneficial physical and/or psychological effects.

1.4.3 Assessment of Potential Risks and Benefits

This study is considered low risk to participants. It is non-invasive and offers a variety of resources for chronic pain management that are not commonly part of standard pain care. It incorporates evidence-based strategies that may improve health and functioning. If the program is effective, it has the potential to be a useful adjunct to clinical care. Overall, given that the potential risks of participation are minimal, the potential benefits outweigh the potential risks.

2 OBJECTIVES & ENDPOINTS

OBJECTIVES	ENDPOINTS	JUSTIFICATION FOR ENDPOINTS
Primary		
To determine if participating in the STEP-UP intervention leads to decreased pain interference with daily functioning.	PROMIS Pain Interference 6a scale is the primary endpoint (pain interference is assessed at baseline, and 8 weeks from baseline). A 2.5 point difference in T-score is considered clinically significant.	Pain interference is a patient-centered outcome that indicates pain's impact on valued and necessary activities. This intervention teaches skills such as goal setting to gradually increase engagement in daily activities.
Secondary		
To determine if participating in the STEP-UP intervention leads to greater improvement in Global Impression of Change in Pain and Functioning.	Patient Global Perception of Change since baseline will be assessed at 8 weeks. Participants will be asked about pain and functioning in separate items.	“Global impression of change” variables capture participants’ subjective perceptions of intervention benefit.

To assess participant engagement in the intervention.	Number of sessions (out of 7) completed at 8 weeks from baseline.	Given the novel nature of this intervention and the barriers that many participants may experience to engagement, it is important to assess whether the intervention as designed yields acceptable engagement levels.
To assess participant satisfaction with the intervention.	Items ask about overall satisfaction with the program, e.g., whether participation increased understanding of pain management (1= Strongly Disagree to 5= Strongly Agree). A higher score indicates higher patient satisfaction.	These items will facilitate understanding of the intervention's acceptability in the priority population as well as highlight potential areas for improvement prior to a larger trial or another future iteration of the intervention.

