3 STUDY DESIGN

3.1 Study Design

- NIH Behavioral Intervention Stage 1 randomized pilot trial to examine the acceptability and preliminary effects of the STEP-UP program on pain interference among older adults with chronic pain compared to a control group.
- Participants will be allocated into the two study arms in a 1:1 ratio by block randomization with mixed block sizes.

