11 STATISTICAL CONSIDERATIONS

11.1 Sample Size

This pilot study is not powered to determine the statistical significance of effects.

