11.2.2 Primary & Secondary Endpoints

We will calculate baseline descriptive statistics and compare groups using independent-sample t-tests for continuous variables and chi-squared tests for categorical variables. We will assess psychometrics of scales used (e.g., internal consistency reliability and concurrent validity). We will convert the PROMIS 6-item Pain Interference subscale score to T-scores (a standardized score with a mean of 50 and SD of 10) by summing the scales and using the conversion tables provided at HealthMeasures.net.

To assess the effect of being in the intervention group, we will use a univariate analysis of variance model for continuous primary and secondary outcomes. The dependent variable in each model will be the value of the outcome at 8-week follow-up; the independent factor will be treatment group (intervention vs. control), with the baseline value of the outcome as a covariate.

Effect size will be indicated by partial eta squared for the treatment group variable. In order to assess the potential clinical relevance of the intervention, we will use chi-squared tests to compare the percentage of participants in each treatment condition who achieved the Minimally Important Difference (MID) of ≥ 3 T-score points in PROMIS pain interference.

We will repeat this analysis with the secondary outcomes: Global Impression of Change in Pain and Functioning. Transformations for non-normality of outcomes will be performed as indicated.

We will also assess the moderating effect of selected variables such as sex, age, baseline pain intensity, and degree of program engagement. Moderation analyses will use standard approaches to evaluate interactions between these covariates and treatment group.

For patient engagement, the secondary outcome indicating feasibility that is composed of: 1) number of sessions completed out of 7; and 2) participant satisfaction on a 5-point Likert scale, we will calculate descriptive statistics. We will also explore differences by age group (under 65/65+) as well as gender. As an exploratory analysis, we will investigate whether satisfaction differs according to whether or not participants achieved the MID on the primary outcome of pain interference.

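### The primary objective asks whether STEP-UP reduces pain interference, but the pilot can only estimate that effect, and Section 11.2.2 plans no interval estimate.

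*Combined protocol and SAP*

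**What the plan says.** The objectives table in Section 2 makes the PROMIS Pain Interference scale the primary endpoint, with the objective "To determine if participating in the STEP-UP intervention leads to decreased pain interference with daily functioning". It adds "A 2.5 point difference in T-score is considered clinically significant".

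Section 11.1 consists of one sentence: "This pilot study is not powered to determine the statistical significance of effects". Section 3.1 describes the trial as one "to examine the acceptability and preliminary effects of the STEP-UP program", and Section 1.1 likewise refers to feasibility and preliminary efficacy. The Protocol Summary gives the size: "We will conduct a randomized (waitlist) pilot trial (n=40) in a Federally Qualified Health Center". Allocation is 1:1 (Section 3.1), so about 20 per arm.

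Section 11.2.2 compares the arms on the 8-week score with the baseline value as covariate and names partial eta squared as the effect size. It continues: "In order to assess the potential clinical relevance of the intervention, we will use chi-squared tests", applied to the share of each arm reaching the "Minimally Important Difference (MID) of ≥ 3 T-score points in PROMIS pain interference".

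The documents give no significance level, no planned confidence interval, no expected precision and no rule for reading a non-significant primary result.

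**The concern.** The primary objective is worded as a yes/no causal question, while the sample size section says the trial was not sized to answer it by a significance test. That disclaimer does not carry through to the analysis. Two of the three planned summaries are tests. The third, partial eta squared, has no sign and is not in T-score points, so it cannot be set against the 2.5 or 3 points that the plan itself calls important. A chi-squared p-value likewise does not say how large the responder difference is or how uncertain it is.

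At stake is how the result feeds into a later study, which Section 2 mentions when justifying the satisfaction endpoint. If the only inferential outputs are p-values, a non-significant result may count against a programme whose data still allow a worthwhile benefit.

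**Working it through.** The plan has no sample size calculation to reproduce. The check is therefore what 20 per arm can deliver at the plan's own thresholds.

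**Inputs from the documents:** 20 per arm (Protocol Summary and Section 3.1); differences of 2.5 points (Section 2) and 3 points (Section 11.2.2); SD 10, which is the PROMIS reference SD in Section 11.2.2 and not a trial estimate; baseline-adjusted comparison.

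**Assumed:** two-sided 0.05; baseline to 8-week correlation r of 0.5 to 0.7; SD 7 as a smaller alternative, with 5 and 6 as sensitivity values; no dropout unless stated.

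**Formulas:** SE = SD × √(1 − r²) × √(2/20). The 95% half-width is 2.026 × SE (t on 37 df). Power is from the noncentral t with noncentrality difference/SE.

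Example, SD 10 and r = 0.5: SE = 10 × 0.866 × 0.316 = 2.74; half-width = 2.026 × 2.74 = 5.5.

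| SD | r | SE | 95% half-width | Power at 2.5 | Power at 3 |
|---|---|---|---|---|---|
| 10 | 0.5 | 2.74 | 5.5 | 14% | 19% |
| 10 | 0.7 | 2.26 | 4.6 | 19% | 25% |
| 7 | 0.5 | 1.92 | 3.9 | 25% | 33% |
| 7 | 0.7 | 1.58 | 3.2 | 34% | 46% |
| 6 | 0.5 | 1.64 | 3.3 | 32% | 43% |
| 6 | 0.7 | 1.36 | 2.7 | 44% | 58% |
| 5 | 0.5 | 1.37 | 2.8 | 43% | 57% |
| 5 | 0.7 | 1.13 | 2.3 | 58% | 74% |

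Power exceeds 50% only in the last rows: for 3 points at SD 6 with r = 0.7 or at SD 5, and for 2.5 points at SD 5 with r = 0.7.

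**Dropout.** Section 6.10 does not replace randomised participants who fail to start or who withdraw. With 17 per arm (assumed), power at 2.5 points and SD 10 falls to 13% to 17%.

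**What the planned outputs would show.** Suppose the observed adjusted difference is exactly 3 points in favour of STEP-UP.
- At SD 10 and r = 0.5, t = 3/2.74 = 1.10. Partial eta squared = t²/(t² + 37) = 1.20/38.20 = 0.03, with p above 0.05.
- The unreported interval would be 3 ± 5.5, or −2.5 to 8.5 points.
- At SD 7 and r = 0.7 it would be 3 ± 3.2, or −0.2 to 6.2 points.

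Both intervals contain zero and both of the plan's thresholds. The eta value and the p-value do not reveal this.

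**Responder test.** Assume a normal change score with SD × √(2(1 − r)), no mean change in controls, and a 3-point threshold. At SD 10 and r = 0.5 the change SD is 10. The control responder rate is then P(Z > 0.3) = 38%, against 50% with a true 3-point shift, and power is about 11%. Over shifts of 2.5 to 3 points, SD 6 to 10 and r 0.5 to 0.7, power runs from 9% to 34%.

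**The case against.** The strongest reply is that the plan already discloses its limits. The title calls it a pilot and feasibility study, the summary calls it Stage 1, Sections 1.1 and 3.1 say preliminary, and Section 11.1 disclaims power. Aim 2 in Section 1.3 speaks of assessing changes, not of proving efficacy. On this view only one table entry is out of line. This largely stands: the trial does not hide its limits, and 40 participants is not itself an error for a pilot.

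A reader might infer that the design cannot produce a significant result, or that a non-significant one will be reported as a failed primary outcome. The documents support neither. Section 11.1 says the trial is not powered for significance, which is weaker than saying it cannot reach it, and a larger true effect or a small SD could do so. No alpha or success rule turns a null result into an unmet objective.

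It is also fair that the chi-squared test only supplements the adjusted model, that responder percentages are an ordinary descriptor of relevance, and that the power figures rest on an assumed SD and correlation. Eligibility restricted to high-impact pain (Section 5.1) may make the SD smaller than 10.

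What remains unanswered is that, whatever the SD, Section 11.2.2 plans no interval for the mean difference or the responder difference. The disclaimer in Section 11.1 does not supply one.

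**Conclusion.** The point holds as a mismatch between the stated objective, the design and the planned summaries. It is not a fault in the sample size. With 20 per arm, two-sided 0.05 and r of 0.5 to 0.7, a true difference of 2.5 to 3 points would reach significance about 14% to 25% of the time at SD 10 and 25% to 46% at SD 7. The corresponding 95% half-widths are 4.6 to 5.5 and 3.2 to 3.9 points, all wider than the plan's own thresholds. The conclusion that non-significance is likelier than not reverses only at an SD of about 6 or less, with higher correlations or the 3-point effect. Alpha, correlation and any SD other than the scale norm are assumptions. The risk is misreading a null result as no benefit; it is not a predicted failure. The change is worth making because it costs almost nothing and affects what the trial can tell its successor.

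**What to change.** - **Section 2:** reword the primary objective as estimating the between-arm difference in 8-week pain interference, to inform a larger trial. This brings it into line with Sections 1.1, 3.1 and 11.1.
- **Section 11.2.2, primary result:** report the baseline-adjusted mean difference in T-score points with its 95% confidence interval. Keep partial eta squared as a supplement if wanted.
- **Section 11.2.2, responders:** replace the chi-squared p-value with the difference in responder proportions and a 95% confidence interval, for example Newcombe's.
- **Section 11.1:** state the expected precision, about ±3 to ±6 T-score points, with the SD (7 to 10) and correlation (0.5 to 0.7) labelled as assumptions. Add that no conclusion of benefit or of no benefit will rest on a p-value.
- While editing, reconcile or explain the 2.5-point figure in Section 2 and the 3-point figure in Section 11.2.2, since the interval will be read against them.

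The cost is protocol and SAP wording, with no change to sample size, data collection or participant burden. The downside is a more modest stated objective.
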